Official Title: Evaluation of Artificial Intelligence for Adenoma Detection in Water Exchange Colonoscopy: the WEAID Randomized Controlled Trial (Water Exchange With Artificial Intelligence-assisted Detection)

NCT number: 06173258

Date of Document: Oct 1, 2023.

Introduction

Adenoma detection rate (ADR) and adenoma per colonoscopy (APC) are crucial predictors for postcolonoscopy colorectal cancer (CRC). Water Exchange (WE) colonoscopy maximizes bowel cleanliness during insertion and has demonstrated superiority in increasing ADR and APC as compared to air insufflation.

Artificial intelligence (AI) lesion computer-aided detection (CADe) devices present promising tools for colonoscopies. Meta-Analysis reveals that AI generates an average ADR gain of 8% and an average APC gain of 0.20 in air-insufflated colonoscopy.

Recent research confirmed that the addition of AI to WE elevated ADR, and the application of WE to AI reduced false positive (FP) instances per colonoscopy, as evidenced by the analysis of pre-recorded video in a randomized controlled trial (RCT) comparing WE and air insufflation. Pilot retrospective data involving 715 patients (367 in the AI group, 348 in the control group) from Italy and Taiwan, with a mean age of 59.6 years (51.5% men) showed that WE with AI demonstrated numerical APC enhancement (1.31 ± 1.80 vs. 1.14 ± 1.38 , $P = 0.152$) and significantly increased the detection rate of proximal sessile serrated lesion (SSL) (5.2% vs. 2.3%, $P = 0.044$) in comparison to WE alone (Tables 1 and 2) (Cheng CL et al. Gastrointest Endosc 2024;99:AB17–18).

Table 1. Per-patient ADR and APC in water exchange (WE) with CADe pilot study

Detection of adenomas	WE without CADe (n=348)	WE with CADe (n=367)	P value
Overall ADR, n (%)	203 (58.3)	207 (56.4)	*0.602
Right ADR, n (%)	106 (30.5)	107 (29.2)	*0.703
Proximal ADR, n (%)	132 (37.9)	149 (40.6)	*0.465
Overall APC, mean (SD)	1.14 (1.38)	1.31 (1.80)	[†] 0.152

*Fisher exact test. [†]Student's *t* test

Table 2. Detection of sessile serrated lesions in WE with CADe pilot study

Detection of SSLs	WE without CADe (n=348)	WE with CADe (n=367)	P value
SSL detection rate			
Overall SSL detection rate, n (%)	10/348 (2.9)	21/367 (5.7)	*0.062
Right SSL detection rate, n (%)	7 (2.0)	14 (3.8)	*0.153
Proximal SSL detection rate, n (%)	8 (2.3)	19 (5.2)	*0.044
Detected SSL per colonoscopy			
Right SSL per colonoscopy, mean (SD)	0.02 (0.17)	0.06 (0.36)	[†] 0.062
Proximal SSL per colonoscopy, mean (SD)	0.03 (0.22)	0.10 (0.58)	[†] 0.036

*Fisher exact test. [†]Student's *t* test

Hypotheses

We hypothesize that the combination of WE and AI will significantly increase APC as opposed to WE alone, in patients undergoing screening or surveillance colonoscopy. The primary outcome of this study is APC. We aim to confirm whether the combination of WE with AI achieves a significantly higher APC than WE alone.

Methods

Study design: The WEAID (WE-AI-assisted Detection) trial is a two-arm parallel multicenter RCT designed to compare APC between WE with AI and WE colonoscopy

alone. Patient recruitment will be conducted at three hospitals in Italy and Taiwan (Digestive Endoscopy Unit, CTO Hospital, Iglesias, Italy [primary investigator: [name]]; Digestive Endoscopy and Gastroenterology Unit, Manzoni Hospital, Lecco, Italy [primary investigator: [name]]; and Evergreen General Hospital, Taoyuan, Taiwan [primary investigator: [name]]). Ethical approval will be sought from the Institutional Review Boards of the participating centers. Informed written consent will be obtained from all enrolled patients. The trial has been registered with ClinicalTrials.gov and assigned the identifier NCT06173258 before patient enrollment. The Sepulveda Ambulatory Care Center, VAGLAHS, UCLA in the USA will be a non-recruiting participating site.

Study population: The study population include male and female patients aged 45–75 years at average risk for CRC who plan to undergo colonoscopy for primary screening, postpolypectomy surveillance, and individuals with positive fecal immunochemical test (FIT) or guaiac fecal occult blood test (gFOBT) results. The exclusion criteria incorporate (1) patients with a history of inflammatory bowel disease, hereditary CRC syndrome, serrated polyposis syndrome, CRC, colorectal resection, colonic stricture, or severe comorbid illnesses rendering polypectomy unsafe; (2) patients with colonoscopy contraindications (e.g., acute diverticulitis or toxic megacolon); (3) therapeutic colonoscopy (e.g., hemostasis, removal of a large polyp); (4) emergent colonoscopy; (5) pregnant women or those planning pregnancy; and (6) patients unwilling to participate in the study.

Study investigators: All study investigators will be experts with a minimum of 500 completed WE colonoscopies. Additionally, each investigator will exhibit a minimum baseline ADR of 25%.

Randomization: Enrolled patients will be randomized in a 1:1 ratio to either the WE with AI-assisted colonoscopy (study group) or WE colonoscopy alone (control group). Randomization will be carried out by computer-generated sequences using a block design (four participants per block). Stratification will be based on study sites, colonoscopists, and colonoscopy indications (primary screening, surveillance, and positive FIT or gFOBT).

Artificial intelligence: Commercially available AI system (CAD-EYE, Fujifilm, EU and Taiwan; Endo-AID, Olympus, EU and Taiwan) will be employed. During AI-assisted procedures, the AI will be activated during the withdrawal phase of the procedure, providing a bounding box as output any time a lesion that is suspected to be a polyp is recognized by the CADe device. At each center, expertise in AI was already developed prior to the start of the study.

Data collection: To capture all study data comprehensively, a case record form will be employed. This form, available in written format, will document various aspects of the study, including enrollment procedures, randomization, colonoscopy details, histological results, and safety information. Study investigators and their teams are responsible for completing all sections of a pre-built Microsoft Excel worksheet.

Colonoscopy procedure: Bowel preparation regimens will align with established standard practices at each individual site. The study procedures employ standard high-definition colonoscopy video processors with integrated AI systems. In both arms of the study, insertion and withdrawal of the colonoscope will be executed by the same colonoscopist. The evaluation and grading of bowel preparation quality will

be carried out using the Boston Bowel Preparation Scale scoring system.

During the insertion phase of WE colonoscopy, the air pump will be turned off, while the colon will be irrigated with water using a flushing pump. The WE approach involves the simultaneous infusion of water to facilitate luminal expansion and suction of unclean water during insertion. Any encountered air pockets will be aspirated to ensure optimal WE maneuver in salvage cleaning. Upon reaching the cecum, where most of the water is suctioned to collapse the cecal lumen, the air pump will be opened. All investigators will be asked to adhere to WE technique confirmation of nearly equivalent volumes of water infused and suctioned upon cecal arrival. During the withdrawal phase, air or CO₂ will be insufflated in both arms.

Withdrawal from the cecum will begin in the left lateral position. Similar withdrawal techniques with adequate luminal distention and comprehensive examination will be emphasized. Adhering to prevailing guidelines set by the American and European Societies of Gastrointestinal Endoscopy, a minimum of 6 minutes of clean withdrawal time will be maintained for all colonoscopies across both arms.

During the withdrawal phase, an exhaustive polyp search and subsequent resection will be performed in both study arms. Comprehensive records will be maintained for all detected polyps, capturing size (assessed in comparison with open forceps or snare), precise location, and morphology (classified according to the Paris classification).

False positives of AI: False positive (FP) activation is defined as the identification by AI systems of an area during the withdrawal phase that is not deemed to be a colorectal lesion after re-examination by the colonoscopist. Real-time flagging of FP activation is recorded by investigators and study staff. The NOISE classification will be

used to categorize the causes of FP activations.

Study outcomes: The primary outcome is APC, calculated as the total number of adenomas detected divided by the total number of colonoscopies performed. Secondary outcomes encompass 1) overall ADR, 2) ADR and APC in the right and proximal colon, 3) SSL detection rates, 4) mean number of non-neoplastic lesions resected per colonoscopy, 5) real-time number of FPs per colonoscopy, and 6) procedural times (e.g., insertion time, withdrawal time, and total procedural time).

Sample size calculation: For group comparison, the sample size was determined assuming that the APC of the control group is 0.9. A clinically significant relative increase of 25% in APC was considered. With a two-sided significance level of 5% and 80% power, 376 patients will be required per group (752 randomized patients). Accounting for a 10% overall dropout rate, enrollment of at least 836 patients is planned.

Statistical analysis: Categorical variables are presented as frequencies and percentages and continuous variables as means with standard deviations. The analysis will follow the intention-to-treat approach. Student's *t*-test will be used for continuous variables and chi-square test will be used for categorical variables. Poisson regression will be used to calculate incident rate ratios comparing the APC between the two arms, adjusting for age, sex, body mass index, smoking history, CADe system, and bowel preparation quality. A planned interim analysis will be conducted after the recruitment of approximately 70% of the planned enrollment to determine whether early termination of the study is appropriate to minimize the number of patients in the control group given the less effective, or clearly inferior

treatment. All statistical analyses will be performed using Python version 3.10 (SciPy Library). A *P* value < 0.05 is considered significant.

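### A fixed block of four, printed in the protocol of an open-label trial, makes on average one third of allocations in completed blocks certain to anyone tracking their stratum

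*Combined protocol and SAP*

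**What the plan says.** All references are to the combined protocol and SAP.

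- **Randomization:** "Enrolled patients will be randomized in a 1:1 ratio", and "Randomization will be carried out by computer-generated sequences using a block design (four participants per block". No other block size is mentioned. "Stratification will be based on study sites, colonoscopists, and colonoscopy indications", with three indication levels.
- **Artificial intelligence:** in the AI arm the device is switched on during withdrawal, "providing a bounding box as output any time a lesion that is suspected to be a polyp is recognized by the CADe device". The operator therefore knows the arm.
- **False positives of AI:** "Real-time flagging of FP activation is recorded by investigators and study staff". Some staff therefore know it too.
- **Study design:** "Informed written consent will be obtained from all enrolled patients". Read with the Randomization section, this places enrollment before randomization.
- **Sample size calculation:** "enrollment of at least 836 patients is planned".
- **Statistical analysis:** the Poisson model compares APC between arms, "adjusting for age, sex, body mass index, smoking history, CADe system, and bowel preparation quality". An unadjusted t-test is also listed for continuous variables.

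The document does not say who holds the allocation list, how the next assignment is concealed, or when it is released. The number of colonoscopists is not given.

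**The concern.** In a 1:1 block of four, once two patients have gone to one arm, the rest of the block is forced. An observer needs three things to exploit this: the block size, the past allocations in the stratum, and some influence over who is enrolled next or when. The protocol prints the first. The second is available to an operator who sees every procedure, and stratifying by colonoscopist means that operators need only remember their own cases. The document leaves the third open. Investigators and their teams complete the study worksheet (Data collection), and at least one exclusion, comorbidity judged to make polypectomy unsafe, calls for judgement (Study population).

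Consent before randomization does not close the gap, because a forced slot can be known before the next patient is approached. If patients thought likelier to have adenomas were steered towards one arm, the APC comparison would mix selection with the effect of AI.

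**Working it through.** **Inputs.** Block of 4 and 1:1 ratio (Randomization); 836 planned patients (Sample size calculation); 3 recruiting sites (Study design); 3 indication levels (Randomization). Assumed: a separate sequence per stratum, and 9 strata (one colonoscopist per site × 3 indications) to 60 strata (20 colonoscopists × 3 indications), of equal expected size.

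**The plan's own figure.** 752 / (1 − 0.10) = 835.6, rounded up to 836. This reproduces the planned enrollment. The document gives no figure for predictability.

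**Fixed block of four.** Enumerate the six equally likely orders of two A and two B:

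| Position | Probability that the arm is certain | Probability that the best guess is right |
|---|---|---|
| 1 | 0 | 1/2 |
| 2 | 0 | 2/3 |
| 3 | 1/3 | 2/3 |
| 4 | 1 | 1 |

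- Certain: (0 + 0 + 1/3 + 1) / 4 = 1/3 = 33.3%. If every block were completed, 836 / 3 = about 279 patients.
- Best guess: (1/2 + 2/3 + 2/3 + 1) / 4 = 17/24 = 70.8%, against 50% by chance.

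One third is an expected value. A single block reveals one of four (four of the six orders) or two of four (the other two). The variance per block is (1/3)(2/3) = 2/9, so over 836 / 4 = 209 complete blocks the SD is √(209 × 2/9) = about 7 patients.

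**Unfinished blocks.** If a stratum ends with 0, 1, 2 or 3 patients in its last block, the shortfall against n/3 is 0, 1/3, 2/3 or 2/3. With these equally likely, the mean is 5/12 per stratum. Expected certain allocations = 836/3 − 5S/12, where S is the number of strata:

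| S | Certain, of 836 | Share | Guessed correctly (simulated) |
|---|---|---|---|
| 9 | 274.9 | 32.9% | 70.6% |
| 36 | 263.7 | 31.5% | 70.0% |
| 60 | 253.7 | 30.3% | 69.5% |

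**Randomly varying sizes.** These figures are simulated, with each size equally likely and an observer who knows the set of sizes but not the current one and updates by Bayes' rule. For sizes 4, 6 and 8:

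| Patients per stratum | Certain | Guessed correctly |
|---|---|---|
| 92 (S = 9) | 2.4% | 67.9% |
| 46 (S = 18) | 2.3% | 67.7% |
| 23 (S = 36) | 2.4% | 67.0% |
| 13 (S = 60) | 2.4% | 66.1% |

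0.024 × 836 = about 20 patients. The result depends on the set: about 5% to 6% certain for sizes 4 and 6, and 10% to 11% for sizes 2 and 4.

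**A softer measure.** Under 4, 6 and 8, 34% to 39% of allocations can still be predicted with probability 0.75 or better, depending on stratum size. Under completed fixed blocks of four the share is 33%, all of it certain.

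**The case against.** The strongest reply is that certainty is the wrong yardstick. Someone inclined to steer enrollment does not need it, and by best-guess accuracy varying the sizes gains only about 3 percentage points. From 33.3% and 2.4% a reader might infer a roughly fifteen-fold gain in security. The calculations do not support that: the low figure counts only allocations known with probability 1, and it belongs to sizes 4, 6 and 8. This part of the objection stands. It is why varying the sizes is not enough without a statement on concealment and release.

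A second reply is that any harm is limited. Adenoma counts are unknown at enrollment, indication is a stratification factor, and age, sex, body mass index and smoking are in the Poisson model. The staff who flag false positives are not said to be those who enroll. This also stands in part, but adjustment reaches only measured factors, bowel preparation is graded during the procedure rather than at enrollment, and the unadjusted t-test has no such protection.

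Third, separate sequences per stratum, the number of strata and their equal sizes are assumptions. That is so, and the patient counts above are illustrative. Within completed blocks, the one-third figure needs only the first of these assumptions.

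Finally, a concealment procedure may exist outside this document. If so, writing it in takes one sentence.

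**Conclusion.** The point holds as an avoidable weakness in a stated rule. With a separate sequence per stratum, a fixed and disclosed block of four lets a person who tracks allocations know on average one third of those in completed blocks (30.3% to 32.9% overall for the assumed 60 to 9 strata) and guess about 71%.

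A reader might go further and infer that the APC comparison will be biased. The document does not support that. The risk is zero if nobody who can predict the next arm can influence who is enrolled or when; the document does not settle this, and no size of bias can be derived from it. Nor should one third be read as a maximum, since it is an average. Nor does the point argue against the strata: they balance an outcome that depends on the operator and should stay.

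The benefit of varying the sizes is mainly the removal of certainty. Confidence is medium, because the practical risk turns on procedures that are not described.

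**What to change.** 1. Replace the fixed block of four with randomly varying block sizes, for example 4, 6 and 8. Keep the sizes in a restricted randomization document and out of the investigator protocol. Keep the existing strata. Avoid a set such as 2 and 4, which leaves 10% to 11% of allocations certain to an observer who knows it.
2. Add one sentence to the Randomization section: each allocation is released only after consent and eligibility have been logged and enrollment is irrevocable, from a list that neither the colonoscopist nor the enrolling staff hold.

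Both steps are needed, because guessing stays above chance under any of these block schemes.

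**Cost.** Regenerate the list, move the block sizes to the restricted document and add the sentence. The statistical price is slightly looser balance in small strata: the largest imbalance within a block rises from 2 patients to 4 when a block of 8 is in use.

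### The stated 80% power depends on an unstated dispersion that the pilot data support poorly: rescaled pilot dispersion gives about 56–71% at 376 per arm, and about 81% only if both arms have an SD of 1.09

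*Combined protocol and SAP*

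**What the plan says.** Under Sample size calculation, "the sample size was determined assuming that the APC of the control group is 0.9". The effect to be detected is then given: "A clinically significant relative increase of 25% in APC was considered", which makes the comparison 0.9 against 1.125. The resulting size follows: "With a two-sided significance level of 5% and 80% power, 376 patients will be required per group (752 randomized patients". After a 10% allowance for dropout, "enrollment of at least 836 patients is planned", which is 418 per arm. The paragraph states no SD, variance, distribution or test.

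The Statistical analysis paragraph names two methods that could apply to APC. A Student's t-test "will be used for continuous variables and chi-square test will be used for categorical variables", and a covariate-adjusted Poisson regression gives the rate ratio for APC between arms. It does not say which is primary or which one the power refers to, and it mentions no robust or scaled standard errors. It also states: "The analysis will follow the intention-to-treat approach".

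The only APC variability in the documents is in the Introduction (text and Table 1): "Pilot retrospective data involving 715 patients (367 in the AI group, 348 in the control group", with "numerical APC enhancement (1.31 ± 1.80 vs. 1.14 ± 1.38". The sample size paragraph does not cite this pilot as its source.

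**The concern.** A sample size for a mean count is not determined until a variance is given, so 376 cannot be traced from the stated inputs. The variance it implies is lower than the pilot suggests, and the AI arm was the more variable of the two.

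What is at stake depends on the test. With a t-test or an overdispersion-corrected rate ratio, a true 25% gain could be missed well over 20% of the time, and a null result could be over-read as showing that AI adds nothing to water exchange. With an uncorrected Poisson regression the rejection rate looks right, but the standard error is too small and a positive result could be over-read. APC is the primary outcome, so either misreading would touch the trial's main conclusion.

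**Working it through.** **Inputs.** From Sample size calculation: means 0.9 and 1.125, difference 0.225, two-sided 5%, 80% power, n = 376 per arm; 836/2 = 418 if everyone enrolled is analysed. From the Introduction: control mean 1.14, SD 1.38; AI mean 1.31, SD 1.80. (1.960 + 0.842)² = 7.849. All figures are unadjusted and ignore the interim analysis.

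**1. The plan's own figure.** With n = 7.849 (v0 + v1)/0.225²:
- Poisson variance, difference scale: 7.849 × 2.025/0.050625 = 314.0.
- Poisson variance, log scale: 7.849 × (1/0.9 + 1/1.125)/(ln 1.25)² = 315.3.
- Solving for 376: v0 + v1 = 376 × 0.050625/7.849 = 2.425, a common SD of √(2.425/2) = 1.10. As an overdispersion factor this is 2.425/2.025 = 1.20 (376/315.3 = 1.19 on the log scale).
- Dropout: 752/0.9 = 835.6, rounded to 836. This step reproduces.

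**2. Pilot dispersion.**
- Variance/mean: 1.904/1.14 = 1.67 (control); 3.24/1.31 = 2.47 (AI).
- Negative binomial k = (variance − mean)/mean²: 0.588; 1.125.
- CV: 1.38/1.14 = 1.211; 1.80/1.31 = 1.374.
- Variance ratio, AI to control: 3.24/1.904 = 1.70.

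**3. Power of a test that holds 5%, dispersion rescaled to the planned means m.** Rules: v = (variance/mean) × m; v = m + k m²; v = (CV × m)². Power = Φ(0.225/√((v0 + v1)/n) − 1.96).

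| Dispersion | SD control, AI | 376 per arm | 418 per arm |
|---|---|---|---|
| Control's variance/mean in both arms | 1.226, 1.371 | 66% | 71% |
| Control's k in both arms | 1.173, 1.367 | 68% | 72% |
| Control's CV in both arms | 1.089, 1.362 | 71% | 75% |
| Own variance/mean | 1.226, 1.668 | 56% | 60% |
| Own k | 1.173, 1.596 | 60% | 64% |
| Own CV | 1.089, 1.546 | 64% | 68% |

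Example (control's CV in both arms): v0 = (1.211 × 0.9)² = 1.187; v1 = (1.211 × 1.125)² = 1.855; 0.225/√(3.042/376) − 1.96 = 0.54; Φ = 0.706. Simulated gamma-Poisson counts (20,000 runs per case, 376 per arm) gave t-test power of 56–71% with a type I error of 4.8–5.2%.

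**4. Favourable cases.**
- One rescaled control SD imposed on both arms: SD 1.09 gives 81% at 376 and 85% at 418; SD 1.17 gives 75% and 79%; SD 1.23 gives 71% and 76%.
- Control SD 1.09 with AI variance 1.25 times control: 76% at 376, 80% at 418.
- With control SD 1.09, 80% at 376 needs an AI SD of at most √(2.425 − 1.187) = 1.113, a variance ratio of 1.04.

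**5. Poisson regression with model-based standard errors, 376 per arm.** se_P = √((1/0.9 + 1/1.125)/376) = 0.0729; se_true = √((v0/0.9² + v1/1.125²)/376).
- Rejection under the planned effect, Φ((ln 1.25 − 1.96 se_P)/se_true): 78–82% over the six rows.
- Type I error with both means 0.9 and control-arm dispersion, 2Φ(−1.96/√(v0/0.9)): variance/mean of 1.67, 1.53 and 1.32 under the three rules give 12.9%, 11.3% and 8.8%.

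**6. Covariate gain needed.** To restore 80%, covariates would have to explain 1 − 2.425/(v0 + v1) of the variance at 376. That is 20% (v0 + v1 = 3.042) to 43% (4.286). At 418, where 2.696 replaces 2.425, it is 11–37%.

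**The case against.** The strongest reply is that nothing in the paragraph contradicts itself. Without a variance, 376 is undetermined, not wrong, and one reading recovers it almost exactly: the pilot control SD scaled in proportion to the mean is 1.38 × 0.9/1.14 = 1.09, and a common SD is a usual planning simplification. The plan is intention-to-treat, and the outcome comes from a single colonoscopy, so close to 418 per arm may be analysed. The pilot is retrospective, is not cited as the source, and has a control mean (1.14) different from the planned 0.9. Its SDs also carry sampling error: simulated at the pilot's size, the variance ratio of 1.70 has a 95% range of about 1.13–2.53, and power under the control-CV rule ranges over about 62–79% at 376 and 66–83% at 418. Planned covariates could help too.

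Much of this stands. It means the common-SD case belongs in any restated range and that the lower figures must be labelled as resting on one AI-arm SD. It does not rescue the 80% as written. At 376, the common-SD case needs AI-arm variance to stay almost flat while the mean rises 25%, and the plan does not argue for that. Control-arm dispersion alone, without the AI-arm SD of 1.80, still gives 66–71%.

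The reply that Poisson regression, the method assigned to APC, rejects 78–82% of the time is correct as arithmetic. That rate comes from understating the variance, so it cannot be paired with a 5% level.

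A reader might also infer that the sample size is an arithmetic error, or that the trial is shown to be underpowered and must enrol more patients. The documents support neither: the variance actually used is unknown, and plausible cases reach 80%.

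**Conclusion.** The point holds as one of traceability and weak support. The plan does not give the dispersion or test behind its 80%, and the variance that 376 implies sits below what the documents' only APC data suggest. For a test that holds 5%, the working estimates are 66–71% at 376 per arm (71–75% at 418) with control-arm dispersion in both arms. With each arm's own dispersion they are 56–64% (60–68%), resting on a single pilot SD. The favourable cases reach 80–81%, or 85% with a common SD of 1.09 and all 418 per arm analysed. With the Poisson regression as written, 80% power and 5% significance do not hold together at pilot dispersion.

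This rests on carrying pilot dispersion over to the planned means, which is an assumption, and on no covariate adjustment, whose gain the documents do not quantify. It should be fixed, but it is not disqualifying; confidence is moderate.

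**What to change.** 1. In Sample size calculation, state the SD or dispersion used, where it came from, and the test to which the power refers. If a common SD near 1.10 is kept, explain why AI-arm variance should not rise with the mean when it was 1.70 times control in the pilot.
2. Restate the power as a sensitivity range. Possible wording: *With the dispersion of the retrospective pilot rescaled to means of 0.9 and 1.125, unadjusted power is about 56–71% with 376 analysed per arm, and up to about 81% if both arms have an SD of 1.09 (60–75%, and up to 85%, with 418 per arm).*
3. In Statistical analysis, specify robust or overdispersion-scaled standard errors, or negative binomial regression, for the APC rate ratio.

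No extra enrolment is asked for; the cost is rewording and one line of model specification. The stated power becomes less favourable. The confidence interval for the rate ratio also widens relative to the uncorrected Poisson one: se_true/se_P is 1.21–1.29 at control-arm dispersion, so about 21–29% on the log scale. The change does not raise power; it lets a null or a positive result be read at its proper weight.

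### The plan does not say which test decides APC, and its Poisson model makes no allowance for the overdispersion seen in the pilot (variance 1.67 to 2.47 times the mean)

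*Combined protocol and SAP*

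**What the plan says.** Study outcomes defines the endpoint: "The primary outcome is APC, calculated as the total number of adenomas detected divided by the total number of colonoscopies performed". This is a count per patient, averaged over patients.

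Statistical analysis then names two methods that could apply to it. Student's t-test "will be used for continuous variables and chi-square test will be used for categorical variables". Separately, the section states: "Poisson regression will be used to calculate incident rate ratios comparing the APC between the two arms". The covariates planned for that model are given next: "adjusting for age, sex, body mass index, smoking history, CADe system, and bowel preparation quality". One rule of P < 0.05 closes the section and is tied to neither method. The section also provides for an early look: "A planned interim analysis will be conducted after the recruitment of approximately 70% of the planned enrollment". Nothing says which method decides APC at either analysis, and nothing says how the Poisson standard errors are to be computed.

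The Sample size calculation does not settle the question. It gives a control APC of 0.9, a 25% relative increase, a two-sided 5% level, 80% power and 376 per group, but no SD, dispersion or test. The Introduction reports pilot data with "numerical APC enhancement (1.31 ± 1.80 vs. 1.14 ± 1.38" for AI versus control. Table 1 marks that comparison as a Student's t-test with P = 0.152.

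**The concern.** A Poisson model with its usual model-based errors takes the variance to equal the mean. Adenoma counts vary more than that between patients, and the protocol's own pilot shows it. The rate-ratio interval is then too narrow and its P value too small. A t-test uses the observed variance and does not share the fault.

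The two methods can therefore disagree on the same data, and the disagreement runs one way: Poisson is significant when the t-test is not. With neither the deciding test nor the variance method fixed in advance, a claim that AI raises APC could rest on the analysis that understates the error. The same gap carries into the interim decision on early termination.

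**Working it through.** **Inputs.** From the Introduction and Table 1: control n = 348, mean 1.14, SD 1.38; AI n = 367, mean 1.31, SD 1.80. From the Sample size calculation: APC 0.9 versus 0.9 × 1.25 = 1.125, with 376 per group.

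**The plan's own figures.** A pooled-variance t-test on the rounded pilot summaries gives t = 1.41, P = 0.158, close to the reported 0.152. The 376 per group cannot be traced: pure Poisson formulas give about 314 to 316, and a two-means formula gives 376 only with an SD of about 1.10, which the plan does not state.

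**Pilot dispersion (SD²/mean).** Control: 1.38²/1.14 = 1.67. AI: 1.80²/1.31 = 2.47. Pooled: 2.59/1.227 = 2.11.

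**Pilot comparison by two variance methods.** ln(1.31/1.14) = 0.139, rate ratio 1.15.
- Model-based: SE = sqrt(1/(348 × 1.14) + 1/(367 × 1.31)) = 0.0678; z = 2.05; P = 0.040; 95% CI 1.01 to 1.31.
- Robust: SE = sqrt(1.38²/(348 × 1.14²) + 1.80²/(367 × 1.31²)) = 0.0967; z = 1.44; P = 0.151; 95% CI 0.95 to 1.39.

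The SE ratio is 0.0967/0.0678 = 1.43. Rounding of the pilot means lets the model-based P lie anywhere from about 0.030 to 0.054. The robust and t-test results stay far from 0.05.

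**Level at the planned APC.** Take the negative binomial α = (SD² − mean)/mean² from the pilot. At APC 0.9 the variance/mean ratio is φ = 1 + 0.9α, the interval is too narrow by a factor of √φ, and the true two-sided level is 2 × (1 − Φ(1.96/√φ)). The last three columns are simulated null rejection rates (40,000 trials per row, 376 per arm, one look, no covariates).

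| Pilot dispersion used | α | φ | √φ | Level by formula | Model-based Poisson | Robust Poisson | t-test |
|---|---|---|---|---|---|---|---|
| Control arm's, both arms | 0.588 | 1.53 | 1.24 | 11.3% | 11.5% | 5.4% | 5.3% |
| Each arm its own | – | 1.77 (mean) | 1.33 | 14.1% | 14.1% | 5.1% | 5.0% |
| Pooled | 0.905 | 1.81 | 1.35 | 14.6% | 14.8% | 5.2% | 5.1% |
| AI arm's, both arms | 1.125 | 2.01 | 1.42 | 16.7% | 17.0% | 5.4% | 5.2% |

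If instead the pilot variance/mean ratios themselves (1.67, 2.11, 2.47) hold at APC 0.9, the formula gives 12.9%, 17.7% and 21.3%.

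**How often the two tests disagree (same simulations, same row order).**
- Null, Poisson significant for AI and t-test not: 3.2%, 4.7%, 4.8%, 5.9%.
- 0.9 versus 1.125, Poisson significant and t-test not: 12.9%, 19.0%, 19.0%, 22.4%.
- t-test significant and Poisson not: none in 40,000 under the control, pooled or AI dispersion, null or alternative.

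**Power for 0.9 versus 1.125 (same row order).** Robust Poisson 68.0%, 61.4%, 60.5%, 56.1%. t-test 67.6%, 60.0%, 60.1%, 55.6%. Model-based Poisson shows 78 to 81%, but at the inflated level.

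**Covariates.** If the six covariates absorb half of the excess dispersion (assumption), the formula gives 8.1%, 9.8% and 11.0% for control, pooled and AI dispersion. An adjusted-model simulation (10,000 runs) gives 8.5%, 10.1% and 11.1%, with robust errors at 5.3 to 5.6%. A level of 6% needs φ = 1.086, so the covariates would have to absorb 1 − 0.086/0.53 = 84% (control), 89% (pooled) or 92% (AI) of the excess.

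**The case against.** The strongest reply is that Poisson regression is the only method the plan names for APC, while the t-test line is generic. On the usual reading the specific sentence governs, so the hierarchy is implied. That is a fair reading, but the plan never calls either analysis primary, and its own pilot tested APC by t-test. It also does not help: if Poisson decides, the variance question matters most.

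Second, the plan does not say that model-based errors will be used. This is true, and the 11 to 17% levels hold only if Poisson decides, its errors are model-based, and dispersion is pilot-like. But the section names no correction, so an analyst following it as written would be using the default errors.

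Third, the pilot is retrospective and had a control APC of 1.14 rather than 0.9, so its dispersion may not carry over. The SD of about 1.10 that would reproduce 376 implies a ratio near 1.2 and a Poisson level of about 7%. This stands as a lower scenario, although that SD is inferred, lies below both pilot SDs, and still leaves the level above 5%.

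Fourth, robust Poisson is not the only remedy. A t-test as the deciding analysis, scaled errors or a negative binomial model would also close the gap. This is correct. What matters is that one is fixed in advance.

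**Conclusion.** The concern holds on both counts: no deciding analysis is designated for the primary outcome, and no variance method is given for a count that is overdispersed in the protocol's own data. If model-based Poisson decides, the two-sided level is about 11 to 17% in place of 5%, or about 8 to 11% if the covariates remove half of the excess dispersion. The 17% figure is an upper scenario, with AI-arm dispersion in both arms. If the t-test decides, the level is held and the harm is confined to an unadjusted rate-ratio interval too narrow by a factor of about 1.24 to 1.42. These figures assume pilot-like dispersion, 376 per arm and one look; none includes the interim analysis. Because the point concerns the primary outcome and the remedy is wording, it must be fixed.

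**What to change.** Before the interim analysis, name one primary analysis of APC in Statistical analysis. Suggested text:

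> The primary analysis of APC is log-link Poisson regression with robust (sandwich) standard errors, adjusted for the six covariates listed in this section, with CADe system coded in both arms by the processor used. The rate ratio is reported with its 95% CI and two-sided P value. This test alone decides the primary outcome, at the interim and final analyses. Student's t-test on APC is supportive.

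The coding rule is workable because, under Colonoscopy procedure, "The study procedures employ standard high-definition colonoscopy video processors with integrated AI systems". The covariates are the plan's own. Whether to keep bowel preparation quality, graded at the colonoscopy, or to add the stratification factors is a separate question. So is the interim significance boundary, which this text does not settle.

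The cost is SAP wording and a named regression package. The plan names only SciPy under Python 3.10. SciPy 1.17.1, the version checked, has a two-sample Poisson means test but no Poisson regression; it requires Python 3.11 or later, so the sponsor should confirm this for its own version. A statsmodels Poisson GLM with HC1 standard errors ran without difficulty.

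The interval becomes wider. Unadjusted power for the planned increase is about 56 to 68%, the same as for the t-test, so the fix exposes a shortfall and does not create it. If covariates absorb half of the excess (assumption), simulated robust power is about 68 to 77% (4,000 runs).
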